7.2.1 Methemoglobinemia

If patient is symptomatic or has hypoxia (<92%) requiring oxygen, obtain “spot” methemoglobin level and serial sampling as clinically indicated (based on symptoms such as but not limited to skin discoloration, cyanosis, coma, dysrhythmia, levels can be repeated every 6-8 hours until levels <20%). A repeat spot methemoglobin should be obtained prior to the next triapine dose to determine whether dose modification or further treatment is indicated. Supportive care should be provided as clinically indicated.

Please note, it is the *trend* in the O₂ saturation that is of importance. Since pulse oximetry is known to be unreliable in the presence of significant methemoglobinemia, weight should not be given to a single value alone. In any case where there is significant doubt, serial spot methemoglobins should be obtained (as clinically indicated based on symptoms such as but not limited to skin discoloration, cyanosis, coma, or dysrhythmia and levels can be repeated every 6-8 hours until levels <20%) and consultation as needed.

It is expected that all patients will show a transient rise in methemoglobin (up to 10-15%) while on study but unless accompanied by hypoxia, or symptoms (e.g., dyspnea), no changes to treatment or dose may be required. However, for patients not fitting this pattern, the following guidelines should be followed:

- If methemoglobin is asymptomatic, <20%, and NOT accompanied by hypoxia (oxygen saturation <92%): treat without change in dose.
- **IF** methemoglobin >15% lasts more than 3 hours **OR** if methemoglobin >20% **OR** if oxygen saturation <92%, **THEN**: obtain arterial blood gases (a pO₂ <80 should result in hospitalization and will be counted as DLT). If pO₂ normalizes within 24 hours, retreatment at a lower dose level may be considered by the Principal Investigator at UPCI.

Treatment options for methemoglobinemia could include methylene blue, 1-2 mg/kg IV over five minutes. However, methylene blue is contraindicated in patients with glucose-6-phosphate (G6PD) deficiency, since its pharmacologic action as an electron carrier in the reduction of methemoglobin is itself dependent on the generation of NADPH by G6PD through the hexose monophosphate shunt. Thus, methylene blue may be at best ineffective in such patients and may have the potential to complicate the clinical situation by provoking hemolysis, although this association is less clear. In situations where the use of methylene blue may be contraindicated (e.g., in those individuals who are in the high-risk group (patients of African, Asian or Mediterranean origin/ancestry), who may have had a false negative G6PD deficiency test, the successful use of ascorbic acid (1000 mg IV q6h) has been described.

8. PHARMACEUTICAL INFORMATION

A list of the adverse events and potential risks associated with the investigational or commercial agents administered in this study can be found in Section 10.1.

8.1 CTEP IND Agent - Triapine

8.1.1 Triapine (NSC # 663249)

Chemical Name: 3-aminopyridine-2-carboxaldehyde thiosemicarbazone

Other Names: 3-AP

Classification: Triapine, an α -heterocyclic carboxaldehyde thiosemicarbazone (HCT), is a ribonucleotide reductase (RNR) inhibitor that acts on the M2 (R2) subunit. The HCTs are the most potent RNR inhibitors, being 65 -5,000 times more potent than hydroxyurea.

Mechanism of Action: Ribonucleotide reductase (RNR) inhibitor

CAS Registry Number: 143621-35-6

Molecular Formula: C₇H₉N₅S **M.W.:** 195

Approximate Solubility: Water = 0.1 mg/mL
Ethanol = 1.25 mg/mL
PEG-300 = 15 mg/mL

How Supplied: Triapine Capsules are supplied by Nanopharmaceutics, LLC and distributed by the CTEP, DCTD, NCI. Each triapine Capsule contains 50 mg of triapine in combination with Starch 1500 and Magnesium Stearate in a size 1, hard gelatin, white, opaque capsule. Each bottle contains 30 capsules.

Storage: Store triapine Capsules at room temperature 25°C, excursions permitted to 15°C to 30°C.

If a storage temperature excursion is identified, promptly return triapine Capsules to between 15 and 30°C and quarantine the supplies. Provide a detailed report of the excursion (including documentation of temperature monitoring and duration of the excursion) to [contact] for determination of suitability.

Stability: Shelf-life stability studies of triapine Capsules are on-going.

Route of Administration: Oral administration. Patients will be asked to fast (except for water) for 2 hours prior to dosing and for 1 hour after ingesting the oral dose. Capsules should not be opened.

Availability

Triapine is an investigational agent supplied to investigators by the Division of Cancer Treatment and Diagnosis (DCTD), NCI.

If the study agent is provided by the NCI under a Collaborative Agreement with the agent manufacturer, the text below must be included in the protocol. Information on the study agent's Collaborative Agreement status will be provided in the approved LOI response letter.

Triapine is provided to the NCI under a Collaborative Agreement between the Pharmaceutical Collaborator and the DCTD, NCI (see Section 13.5).

8.1.2 Agent Ordering and Agent Accountability

8.1.2.1 NCI-supplied agents may be requested by eligible participating Investigators (or their authorized designee) at each participating institution. The CTEP-assigned protocol number must be used for ordering all CTEP-supplied investigational agents. The eligible participating investigators at each participating institution must be registered with CTEP, DCTD through an annual submission of FDA Form 1572 (Statement of Investigator), NCI Biosketch, Agent Shipment Form, and Financial Disclosure Form (FDF). If there are several participating investigators at one institution, CTEP-supplied investigational agents for the study should be ordered under the name of one lead participating investigator at that institution.

In general, sites may order initial agent supplies when a subject is being screened for enrollment onto the study.

Submit agent requests through the PMB Online Agent Order Processing (OAOP) application. Access to OAOP requires the establishment of a CTEP Identity and Access Management (IAM) account and the maintenance of an "active" account status, a "current" password, and active person registration status. For questions about drug orders, transfers, returns, or accountability, call or email PMB any time. Refer to the PMB's website for specific policies and guidelines related to agent management.

8.1.2.2 **Agent Inventory Records** – The investigator, or a responsible party designated by the investigator, must maintain a careful record of the receipt, dispensing and final disposition of all agents received from the PMB using the appropriate NCI Investigational Agent (Drug) Accountability Record (DARF) available on the CTEP forms page. Store and maintain separate NCI Investigational Agent Accountability Records for each agent, strength, formulation and ordering investigator on this protocol.

8.1.3 Investigator Brochure Availability

The current versions of the IBs for the agents will be accessible to site investigators and research staff through the PMB OAOP application. Access to OAOP requires the establishment of a CTEP IAM account and the maintenance of an "active" account status, a "current" password and active person registration status. Questions about IB access may be directed to the PMB IB Coordinator via email.

8.2 Commercial Agent - Lutetium Lu 177 Dotatate (NSC 815530)

Product description:

Lutetium Lu 177 Dotatate injection containing 10 mCi/ml of Lutetium Lu 177 Dotatate is a sterile, preservative-free and clear, colorless to slightly yellow solution for IV use supplied in a colorless Type I glass 30 mL single-dose vial containing 200 mCi \pm 10% of Lutetium Lu 177 Dotatate at the time of injection. The solution volume in the vial is adjusted from 20.5 mL to 25 mL to provide a total of 200 mCi of radioactivity. Each single-dose vial contains acetic acid (0.48 mg/mL), sodium acetate (0.66 mg/mL), gentisic acid (0.63 mg/mL), sodium hydroxide (0.65 mg/mL), ascorbic acid (2.8 mg/mL), diethylene triamine pentaacetic acid (0.05 mg/mL), sodium chloride (6.85 mg/mL), and Water for Injection (ad 1 mL). The pH range of the solution is 4.5 to 6.

Solution preparation:

Lutetium Lu 177 Dotatate is a radiopharmaceutical; handle with appropriate safety measures to minimize radiation exposure. Use waterproof gloves and effective radiation shielding when handling Lutetium Lu 177 Dotatate. Radiopharmaceuticals, including Lutetium Lu 177 Dotatate, should be used by or under the control of physicians who are qualified by specific training and experience in the safe use and handling of radiopharmaceuticals, and whose experience and training have been approved by the appropriate governmental agency authorized to license the use of radiopharmaceuticals.

- Use aseptic technique and radiation shielding when administering the Lutetium Lu 177 Dotatate solution. Use tongs when handling vial to minimize radiation exposure.
- Do not inject Lutetium Lu 177 Dotatate directly into any other IV solution.
- Confirm the amount of radioactivity of Lutetium Lu 177 Dotatate in the radiopharmaceutical vial with an appropriate dose calibrator prior to and after Lutetium Lu 177 Dotatate administration.
- Inspect the product visually for particulate matter and discoloration prior to administration under a shielded screen. Discard vial if particulates or discoloration are present.

- Insert a 2.5 cm, 20 gauge needle (short needle) into the Lutetium Lu 177 Dotataate vial and connect via a catheter to 500 mL 0.9% sterile sodium chloride solution (used to transport Lutetium Lu 177 Dotataate during the infusion). Ensure that the short needle does not touch the Lutetium Lu 177 Dotataate solution in the vial and do not connect this short needle directly to the patient. Do not allow sodium chloride solution to flow into the Lutetium Lu 177 Dotataate vial prior to the initiation of the Lutetium Lu 177 Dotataate infusion and do not inject Lutetium Lu 177 Dotataate directly into the sodium chloride solution.
- Insert a second needle that is 9 cm, 18 gauge (long needle) into the Lutetium Lu 177 Dotataate vial ensuring that this long needle touches and is secured to the bottom of the Lutetium Lu 177 Dotataate vial during the entire infusion. Connect the long needle to the patient by an IV catheter that is pre-filled with 0.9% sterile sodium chloride and that is used exclusively for the Lutetium Lu 177 Dotataate infusion into the patient.

Route of administration: Lutetium Lu 177 Dotataate is administered IV.

- Use a clamp or pump to regulate the flow of the sodium chloride solution via the short needle into the Lutetium Lu 177 Dotataate vial at a rate of 50 mL/hour to 100 mL/hour for 5 to 10 minutes and then 200 mL/hour to 300 mL/hour for an additional 25 to 30 minutes (the sodium chloride solution entering the vial through the short needle will carry the Lutetium Lu 177 Dotataate from the vial to the patient via the catheter connected to the long needle over a total duration of 30 to 40 minutes).
- Do not administer Lutetium Lu 177 Dotataate as an IV bolus.
- During the infusion, ensure that the level of solution in the Lutetium Lu 177 Dotataate vial remains constant.
- Disconnect the vial from the long needle line and clamp the saline line once the level of radioactivity is stable for at least five minutes.
- Follow the infusion with an IV flush of 25 mL of 0.9% sterile sodium chloride.
- Dispose of any unused medicinal product or waste material in accordance with local and federal laws.

Storage: The product vial is in a lead shielded container placed in a plastic sealed container. The product is shipped in a Type A package. Store below 25 °C (77 °F). The shelf life is 72 hours. Discard appropriately at 72 hours.

Agent Ordering: Lutetium Lu 177 Dotataate is commercially available. For ordering information, please visit: <https://hcp.lutathera.com/ordering-lutathera/>

Lutetium Lu 177 Dotataate, accompanying amino acid infusion as well as supportive care medication can be administered per treating hospital standard operating procedure per standard of care, as approved by FDA.

For additional information, please refer to the package insert.

9. STATISTICAL CONSIDERATIONS

9.1 Study Design/Endpoints

This study is a multicenter phase 1 trial of triapine and Lutetium Lu 177 Dotatace in combination for well-differentiated somatostatin receptor-positive GEP-NETs after the failure of at least one line of prior systemic cancer treatment. An expansion cohort with 14 additional patients will be enrolled at the RP2D to further assess safety, obtain initial estimates of clinical response outcomes, and perform exploratory comparisons of biomarkers.

The primary objective of the **phase 1 trial** is to determine the MTD and identify the RP2D of triapine in combination with Lutetium Lu 177 Dotatace. The Bayesian optimal interval design (BOIN) (Yuan *et al.*, 2016) will be employed to guide dose escalation. DLT is defined in Section 6.2 and will be assessed after the first cycle (8 weeks post treatment). Patients will be enrolled in cohorts of 3 beginning at dose level 1. A target DLT rate of 25% will be assumed with dose escalation, λ_e , and de-escalation boundaries, λ_d , set at 0.197 and 0.298, respectively. Based on the BOIN design, dose escalation will proceed as shown in the table below until a total of 15 patients have been enrolled in the dose escalation part of this phase 1 trial. MTD and RP2D will be estimated using isotonic regression based on toxicity data from all patients.

Dose escalation and de-escalation boundaries Table

Number of patients treated at the current dose:	1	2	3	4	5	6	7	8	9	10	11	12	13	14	15
Escalate if DLTs \leq	0	0	0	0	0	1	1	1	1	1	2	2	2	2	2
De-escalate if DLTs \geq	1	1	1	2	2	2	3	3	3	3	4	4	4	5	5

An expansion cohort with 14 additional patients will be enrolled at the RP2D to further assess safety, obtain initial estimates of clinical response outcomes, and perform exploratory comparisons of biomarkers. Assuming that the minimum number of patients enrolled at the RP2D is equal to 17, the proposed sample size from the phase 1 portion and expansion cohort will produce a two-sided 95% exact confidence interval with a width equal to 0.44, when the DLT rate is 0.25.

Interim Analysis for Phase 1 (Dose escalation)

For the Phase 1 portion of this study, all decisions regarding dose escalation/expansion/de-escalation require sign-off by the Protocol Principal Investigator through the CTMS/IWRS. In addition, for the Phase 1 portion, the Protocol Principal Investigator will have at least bi-monthly, or more frequently, conference calls with the Study Investigators and the CTEP Medical Officer(s) to review accrual, progress, adverse events, and unanticipated problems. DLT will be assessed as defined in Section 6.2 using CTCAE version 5.0 which will be assessed after the first cycle for each patient enrolled in the trial. The dose escalation and cohort sizes are specified in the table above. Automated triggers developed by the Biostatistics and Bioinformatics Shared Resource at Markey Cancer Center (MCC) will be run after each patient is enrolled in order to perform real-time evaluation of DLT to make recommendations to the study team to implement the dose

escalation rule defined in the Table above. The Protocol Principal Investigator will make dose escalation decisions based on evaluation of all patient data, including type of DLT and non-DLT events. The appropriate dose level available for patient enrollment is made available in the OPEN and IWRS system described in Section 4.3.

Expansion Cohort Safety Assessment

For the expansion cohort, patients will continue to be monitored for occurrence of DLT. If 2 of the first 5 patients or if ≥ 2 of 6 patients experience DLT, the PI will discuss with all study investigators and with CTEP whether further addition of patients is needed to re-assess the RP2D; isotonic regression will also be utilized to estimate the DLT rate. Monitoring of all safety and toxicity data is done by the PI and the Corresponding Organization on a real-time basis as data are entered into Medidata Rave using the Web Reporting Module. All participating sites are expected to notify the PI when a DLT has occurred.

Analysis of Safety Data

The MTD will be estimated using isotonic regression based on observed DLT from all patients enrolled in the phase 1 portion and expansion cohort. All patients who received study drugs will be included in the safety analysis. DLTs based on Section 6.2 will be summarized descriptively at each dose level. Adverse events will be summarized based on CTCAE version 5.0. The maximum grade of toxicity for each adverse event category of interest will be recorded for each patient and the summary results will be tabulated by category and grade. We will describe all serious (\geq grade 3) toxicity events on a patient-by-patient basis. Frequency and incidence tables of toxicity and adverse events will be generated in the overall patient group and by dose level depending on patient enrollment.

9.2 Sample Size/Accrual Rate

A total of 29 patients will be enrolled in the dose escalation and dose expansion cohorts. The study will be open through the entire ETCTN for any Lutetium Lu 177 Dotatate compatible site. However, University of Kentucky and Ohio State University are willing to establish the RP2D, using a limited LAO network if requested, before the expansion phase being offered to the entire ETCTN. Both Ohio State University and University of Kentucky offer PPRT therapies. We are currently treating 2-3 patients per week with Lutetium Lu 177 Dotatate at University of Kentucky alone and do not foresee difficulties with accrual to the RP2D. The study is expected to complete accrual in approximately 3 years.

PLANNED ENROLLMENT REPORT

Racial Categories	Ethnic Categories				Total
	Not Hispanic or Latino		Hispanic or Latino		
	Female	Male	Female	Male	
American Indian/ Alaska Native	0	0	0	0	0

Racial Categories	Ethnic Categories				Total
	Not Hispanic or Latino		Hispanic or Latino		
	Female	Male	Female	Male	
Asian	1	1	0	0	2
Native Hawaiian or Other Pacific Islander	0	0	0	0	0
Black or African American	5	5	0	0	10
White	8	8	0	0	16
More Than One Race	1	0	0	0	1
Totals	15	14	0	0	29

PHS 398 / PHS 2590 (Rev. 08/12 Approved Through 8/31/2015)

OMB No. 0925-0001/0002

9.3 Stratification Factors

N/A

9.4 Results of Phase 1: RP2D for the Dose Expansion Cohort

As noted in 9.1, this study includes an expansion cohort upon completion of phase 1 (i.e., dose escalation which determines the RP2D). An expansion cohort with 14 additional patients will be enrolled and treated with the RP2D in order to further assess safety, obtain initial estimates of clinical response outcomes, and perform exploratory comparisons of biomarkers.

9.4.1 Results of the dose escalation phase (interim analysis of Phase 1)

The Phase 1 dose escalation enrolled 15 patients using the BOIN design. Isotonic regression provided posterior estimates of the DLT rate at each dose level. The DLT estimate for DL2 = 0.18, 95% credible interval: (0.03, 0.045) and at DL2 the Prob (DLT rate > 0.25) = 0.25. All evaluable patients completed the DLT window.

9.4.2 Recommended Dose for Dose Expansion Cohort

The RP2D is DL2, **Triapine 150mg once a day during Days 1-14 of each Lu-177 dotatate cycle.**

9.4.3 Plan for Dose Expansion Phase

The dose expansion cohort opened to accrual on 10/08/2021. As noted above in 9.1, patients enrolled in the dose expansion cohort phase will continue to be monitored for occurrence of DLT.

If 2 of the first 5 patients or if ≥ 2 of 6 patients experience DLT, the PI will discuss with all study

investigators and with CTEP whether further addition of patients is needed to re-assess the RP2D; isotonic regression will also be utilized to estimate the DLT rate. Monitoring of all safety and toxicity data is done by the PI and the Corresponding Organization on a real-time basis as data are entered into Medidata Rave using the Web Reporting Module. All participating sites are expected to notify the PI when a DLT has occurred.

9.5 Analysis of Secondary and Correlative Endpoints

ORR will be estimated along with 95% exact binomial confidence interval. PFS and OS will be estimated using the Kaplan-Meier curve and median estimates and confidence intervals will be calculated. Correlative endpoints such as radiographic expression of somatostatin receptors and changes from pre to post-treatment will be summarized using descriptive statistics and changes from baseline *vs.* follow-up time points will be assessed using paired test methodologies. WES data will be processed using the data processing and data analysis pipelines from the Biostatistics and Bioinformatics shared resource of MCC to identify candidate mutated genes with adjustment for false discovery rate. PK analysis will be performed and PK parameters will be estimated from patients enrolled in the dose escalation portion of the phase 1 trial. PK parameters will be compared with historical controls, and exploratorily, we may correlate exposure to toxicity, and incorporate data into a population PK model. Krenning score from the Gallium-68 Dotatate (or Copper-64 Dotatate) will be summarized by calculating the proportion of patients in each Krenning score category and exploratory assessments for association with clinical response (ORR) will be performed using Fisher's exact test. Median, interquartile range will be calculated for quantitative image measurements from Gallium-68 Dotatate (or Copper-64 Dotatate) and exploratory comparison of levels with clinical response (ORR) will be performed using two sample t-test or nonparametric analogs. Mean change in deoxynucleosides between baseline and post treatment samples will be assessed by paired t-test or other methods. Deoxynucleoside plasma concentration as a predictor of clinical outcomes will be explored by linear (progression free survival) and logistic regression (response).

Correlative endpoint analyses will be based on patients who received the RP2D from the dose escalation portion and expansion cohort. See details in Sections 6.3 and 9.4 for RP2D.

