6.3.1 Triapine RP2D

After completion of dose escalation on 15 patients, **Dose Level 2 was selected as the RP2D** for the dose expansion cohort. Thus, all patients enrolled in the dose expansion cohort will be administered **Triapine 150mg** orally once a day on Days 1-14 of each Lu-177 dotatate cycle.

An additional 14 patients will be treated at the RP2D dose (i.e., enrolled in the dose expansion cohort). For the expansion cohort, patients will continue to be monitored for occurrence of DLT. If 2 of the first 5 patients or if ≥ 2 of 6 patients experience DLT, the Principal Investigator will discuss with all study investigators and with CTEP whether further addition of patients is needed to re-assess the RP2D. Monitoring of all safety and toxicity data is done by the Principal Investigator and the Corresponding Organization on a real-time basis as data are entered into Medidata Rave using the Web Reporting Module. All participating sites are expected to notify the Principal Investigator when a DLT has occurred.

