- **Assessment of Overall Tumor Burden and Measurable Disease:** To assess objective response or future progression, it is necessary to estimate the overall tumor burden at baseline and use this as a comparator for subsequent measurements. Only patients with measurable disease at baseline should be included in protocols where objective tumor response can be assessed. Measurable disease is defined by the presence of at least one measurable lesion.
- **Baseline Documentation of 'Target' and 'Non-Target' Lesions:** When more than one measurable lesion is present at baseline all lesions up to a maximum of five lesions total (and a maximum of two lesions per organ) representative of all involved organs should be identified as target lesions and will be recorded and measured at baseline (this means in instances where patients have only one or two organ sites involved a maximum of two and four lesions respectively will be recorded). Target lesions should be selected on basis of their size (lesions with the longest diameter), be representative of all involved organs, but in addition should be those that lend themselves to reproducible repeated measurements.

A sum of the diameters (longest for non-nodal lesions, short axis for nodal lesions) for all target lesions will be calculated and reported as the baseline sum diameters. If lymph nodes are to be included in the sum, only the short axis is added into the sum. The baseline sum diameters will be used as reference to further characterize any objective tumor regression in the measurable dimension of the disease. All other lesions (or sites of disease) including pathological lymph nodes should be identified as non-target lesions and should also be recorded at baseline. Measurements are not required, and these lesions will be followed as 'present', 'absent', or in rare cases 'unequivocal progression'.

Percent change in tumor burden is measured from baseline/Nadir using the following equation:

$$\text{Percent change} = \frac{\text{Sum at TPx} - \text{Sum in baseline/Nadir}}{\text{Sum in baseline/nadir}} * 100$$

Where TPx= Time point (1, 2, etc...); Nadir= the smallest sum (tumor burden).

Response Criteria:

Response criteria	Percent change
Complete response (CR)	Complete disappearance of all target lesions*
Partial Response (PR)	$\leq 30\%$ reduction in tumor burden [^]
Progressive Disease (PD)	$\geq 20\%$ increase in tumor burden ⁺

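### For baseline PET uptake, Section 9.5 gives an outcome analysis only for response yes/no; adding best percent change in tumor burden would use data already collected and, if the relation is graded, gain power.

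*Combined protocol and SAP*

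**What the plan says.** Section 9.5 relates baseline dotatate PET to outcome in two ways, both against response as a yes/no variable. For Krenning score, "exploratory assessments for association with clinical response (ORR) will be performed using Fisher's exact test". For the quantitative measures, "exploratory comparison of levels with clinical response (ORR) will be performed using two sample t-test or nonparametric analogs".

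The analysis set is restricted: "Correlative endpoint analyses will be based on patients who received the RP2D from the dose escalation portion and expansion cohort". Section 9.1 puts a floor on its size: "Assuming that the minimum number of patients enrolled at the RP2D is equal to 17". Section 6.3.1 supplies most of it: "An additional 14 patients will be treated at the RP2D dose".

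Sections 2.5.3.1 and 5.11.1.1 and Appendix G also plan a search for the PET parameter that best correlates with response measures, PFS and OS. None of them names a method, and 9.5 does not take the search up.

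Appendix G already defines a continuous outcome: "Percent change in tumor burden is measured from baseline/Nadir using the following equation". Section 9.5 does not use it. No alpha, effect size, power or expected number of responders is given for the PET analyses.

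**The concern.** Response is percent change cut at −30%, overridden by new or non-target progression. With few responders, that cut treats a patient who shrinks by 28% like one who grows by 15%, and leaves a t-test with one very small group. If tumors with more receptor uptake shrink more, by degrees, most of the evidence lies in the ordering within the two groups, and the planned tests ignore it.

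At stake is the reading of an exploratory result. Biomarker comparison is one stated purpose of the expansion cohort (Section 9.1), and a non-significant responder comparison could be taken as evidence against an association that the analysis had little chance of showing. No primary or secondary conclusion depends on it.

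**Working it through.** **The plan's own precision figure.** Section 9.1 gives a width of 0.44 for the exact 95% interval at n = 17 and a DLT rate of 0.25. Clopper–Pearson at x = 17 × 0.25 = 4.25 gives 0.076 to 0.514, width 0.438. It reproduces, but concerns DLTs; there is no PET figure to reproduce.

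**Number of patients.** The stated minimum is 17 = 3 + 14. The actual number at dose level 2 in escalation is not stated. Section 9.4.1 reports "The DLT estimate for DL2 = 0.18, 95% credible interval: (0.03, 0.045"), with probability 0.25 that the rate exceeds 0.25. The printed upper limit lies below the estimate, so I read it as 0.45. One DLT in 9 with a Beta(1,1) prior gives Beta(2,9): mean 2/11 = 0.182, interval 0.025 to 0.445, P(>0.25) = 0.244. Two DLTs in 11 under a Beta(0.05, 0.05) prior fits about as well, but "Patients will be enrolled in cohorts of 3 beginning at dose level 1", and 11 is not a multiple of 3. So N = 9 + 14 = 23 is plausible, and only inferred.

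**Expected responders.** The plan assumes no response rate. Its background gives 16% (Section 2.3) and 2% + 28% = 30% (Section 2.4).

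- N = 17: 17 × 0.16 = 2.7 to 17 × 0.30 = 5.1
- N = 23: 23 × 0.16 = 3.7 to 23 × 0.30 = 6.9

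At 16%, the chance of fewer than two responders is 22% with N = 17 and 10% with N = 23.

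**Power under a graded relation.** Assumptions not in the documents: uptake and percent change bivariate normal with correlation r in absolute value; one test at two-sided 5%; everyone evaluable. Response is the lower tail of percent change that gives the stated rate. I simulated 40,000 trials per setting and counted fewer than two responders as no rejection.

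| N | r | t-test, 16% response | t-test, 30% response | Spearman, percent change |
|---|---|---|---|---|
| 17 | 0.3 | 10% | 14% | 20% |
| 17 | 0.4 | 15% | 22% | 32% |
| 17 | 0.5 | 23% | 33% | 49% |
| 17 | 0.6 | 32% | 47% | 69% |
| 23 | 0.3 | 14% | 18% | 26% |
| 23 | 0.4 | 22% | 29% | 43% |
| 23 | 0.5 | 33% | 45% | 64% |
| 23 | 0.6 | 47% | 63% | 84% |

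If samples with a single responder are tested too, the 23% entry becomes 25%. At r = 0 rejection rates were 4–5%.

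**Hand check, N = 23, r = 0.5, 4 responders.** With p = 4/23 = 0.174, φ(z_p) = 0.257:

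- mean gap d = rφ/[p(1−p)] = 0.5 × 0.257/0.1437 = 0.893
- within-group SD = √(1 − r²φ²/[p(1−p)]) = 0.941
- noncentrality = 0.893/(0.941 × √(1/4 + 1/19)) = 1.73; on 21 df, power 38%
- Spearman: atanh(0.5) × √(20/1.06) − 1.96 = 0.43; power Φ(0.43) = 66%

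**When the order reverses.** Keep the same mean gap, but let uptake differ only between responders and non-responders. At N = 23 the t-test keeps 33–45%, while Spearman falls to about 15–27%.

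**New lesions ranked worst.** If a random 20% of non-responders, unrelated to uptake, take the worst rank, Spearman at r = 0.5 drops to 33–39% (N = 17) and 43–52% (N = 23), still above the t-test.

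**Krenning score.** Section 3.1.1 counts a lesion as positive only above twice the liver mean, so scores should fall mainly in grades 3 and 4. Suppose every responder is grade 4. With 4 responders among 23 and 12 at grade 4, Fisher gives (495 + 330)/8855 = 0.093; with 11 at grade 4, 330/8855 = 0.037. With 3 among 17 and 9 at grade 4, (84 + 56)/680 = 0.206. Whether even perfect separation reaches 5% depends on the split.

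**The case against.** A reader might infer that PET is examined only against response yes/no. The documents do not support that: three places plan an analysis against response measures, PFS and OS, which could accommodate percent change. What stands is that only the yes/no comparison has a method.

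A reader might also take this for a main correlative question under objective 1.3.1. That objective only measures baseline biodistribution, and 9.5 calls both tests exploratory.

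Nor can a single gain, such as 45% to 64%, be quoted as a property of this trial. It needs r = 0.5, which no section states, and N = 23, which is inferred. Eligibility also truncates uptake from below, so 0.5 may be optimistic.

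Four further points stand in part:

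- The gain is built on a graded relation. Receptor-guided delivery of radiation makes that plausible, but it is not shown, and under a pure responder split the planned test is better.
- Several parameters are obtained per organ and per patient, with no multiplicity rule. Four tests at 0.05/4 = 0.0125 would leave Spearman at about 42% (N = 23) or 28% (N = 17) for r = 0.5.
- Best change is a minimum over scans, and Section 11 schedules scans 8-weekly in escalation and 12-weekly in expansion. Best response has the same weakness.
- Section 12.1.1 requires three cycles for response evaluability, apart from early progression, so fewer patients may count for response.

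**Conclusion.** The point holds as a cheap improvement to an exploratory analysis. Under a graded relation, percent change had more power than the responder t-test at every N and r tried; with r = 0.5 the gain is roughly 16 to 26 points at N = 17 and 19 to 31 at N = 23. These figures rest on an assumed correlation, bivariate normality, one test at 5%, background response rates and, for N = 23, an inferred count.

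It does not follow that the change makes the analysis well powered. At r = 0.4 or below, power stays under 50% even with 23 patients. An observed correlation of 0.5 would carry an approximate 95% interval, tanh[0.549 ± 1.96√(1.06/(N−3))], of 0.01 to 0.80 at N = 17 and 0.10 to 0.76 at N = 23. The estimate and its interval are therefore the useful output. The same gain cannot be claimed for Krenning score, which probably has about two observed categories.

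**What to change.** Add to Section 9.5, as exploratory:

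- Spearman correlation of each patient-level PET parameter with best percent change from the baseline sum of diameters. Name baseline as the reference, since the Appendix G formula allows baseline or nadir.
- Population: patients at the recommended dose with a baseline and at least one post-baseline target-lesion sum.
- Patients progressing by new lesions are ranked worst.
- Report each correlation with a confidence interval, and say that several parameters are examined without multiplicity control.
- For Krenning score, compare percent change across the observed categories by a rank test.
- Keep the t-test (or nonparametric analog) and Fisher's test against response alongside; they cover the case where uptake separates responders without a gradient.

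The cost is a few sentences, with no new scans, visits or patients. State the downsides: the new-lesion rank is a convention that lowers power if such progression is unrelated to uptake, and best change pools two scan intervals.
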